6.1.1 Study Population and Design

This is a phase 3, multicenter, randomized, double-blind, parallel-group study to evaluate the efficacy of TAK-385 40 mg administered orally once daily for 12 weeks compared with placebo in subjects having pain symptoms associated with uterine fibroids.

Subjects must have a diagnosis of uterine fibroids confirmed by transvaginal ultrasound or other methods. Subjects must experience pain symptoms (eg, lower abdominal pain and low back pain) with intensity of ≥ 1 on the NRS score for at least 2 days during 1 menstrual cycle, of which at least one of the intensities should be at least moderate (NRS score of ≥ 4). The total number of subjects to be randomized under double-blind conditions is 64 (32 subjects each for the TAK-385 40 mg group or placebo group).

[figure not shown]
After signing the informed consent form, subjects will start recording in the patient diary from the day of VISIT 1. During the period between VISIT 2 and VISIT 3, in which subjects must experience 1 menstrual cycle, the baseline values for the efficacy evaluation of pain symptoms (baseline NRS score: the maximum NRS score for the entire menstrual cycle immediately before VISIT 3.) will be collected. Subjects should record in the patient diary every day until the end of study drug administration. VISIT 2 should be between the first and fifth day of the first menstruation after VISIT 1. The study drug (TAK-385 placebo) will be administered under single-blind conditions from the day of first menstruation after VISIT 1 to the day before VISIT 3. VISIT 3 should be between the first and fifth day of the second menstruation after VISIT 1. From VISITS 2 to 6, subjects should try to visit the study site during the morning in a fasted state and before taking the study drug.

This study consists of Screening of approximately 1 to 6 weeks, a Run-in period of 3 to 6 weeks, a Treatment period of 12 weeks, and a Follow-up period of 4 weeks. The total period of study participation is approximately 20 to 28 weeks. If the recovery of the first post-treatment menstruation is not observed by the visit at the end of the Follow-up (VISIT 7), the subject will undergo further follow-up using possible means such as by telephone interview, until the recovery of the first post-treatment menstruation is observed. During the course of this study, subjects will visit the study site to undergo the designated examinations and evaluations at each visit.

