11. The subject should take study drugs every day before breakfast during the Run-in and the Treatment, and should try to take the study drug at approximately the same time each day. If the subject forgets to take the study drug before breakfast, she should take it before lunch on the same day. If the subject forgets to take the study drug in both cases (ie, before breakfast and before lunch), she should take it before dinner on the same day. The subject should avoid carrying over the missed dose to other day and taking multiple doses together on the same day. The date of administration and whether the drug was taken before a meal should be properly recorded in the patient diary.

For the scheduled study site visit from VISIT 2 through 6, follow the instructions below:
<VISIT 2, 3 and 6>

On the days of the scheduled study site visit, the subject should try to visit the study site without taking the TAK-385 tablet in the morning and undergo the designated study procedures as far as possible. Even if the subject cannot visit the study site in the morning, she should still come to the study site without taking the TAK-385 tablet.

<VISIT 4 and 5>

On the days of the scheduled study site visit, the subject should try to visit the study site without taking the TAK-385 tablet in the morning and undergo the designated study procedures as far as possible. If the subject cannot visit the study site in the morning, she must take the TAK-385 tablet before breakfast, and report to the investigator or subinvestigator that she has taken the drug.

12. When the subject needs to take analgesic drugs due to severe pain associated with uterine fibroids, the subject should comply with the investigator's or subinvestigator's instructions before taking the analgesic drug, and try to avoid taking it in a fasted state as far as possible. The subject should also not take the analgesic drug casually or for prophylactic purposes. In cases where the subject has to take an analgesic drug, she is required to properly record her pain symptoms which occur before taking analgesics in the patient diary (NRS) and to record analgesic use in the patient diary.
13. The subject may use acetaminophen as the first choice medicine in certain circumstances, such as occurrence of an AE, that requires an analgesic for purposes other than to relieve pain from uterine fibroids. In this case, avoid casually using it for prophylactic purposes.

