9.3.4 Follow-up

9.3.4.1 VISIT 7 (*Final visit of the Follow-up, 28 days after last dose*)

The Follow-up lasts for 4 weeks (28 days) from the day after the final dose of study drug. The following procedures should be performed at the final visit of the Follow-up (VISIT 7). If early termination occurs during the Treatment, the same procedures scheduled at VISIT 7 should be performed 4 weeks (28 days) after the end of treatment. If study termination occurs during the Follow-up, the same procedures scheduled at VISIT 7 should be performed.

- Pregnancy test (urine)
- Physical examination
- Vital signs and weight
- Status of menstruation recovery
- Clinical laboratory tests
- Pharmacodynamic measurements
- Standard 12-lead ECG
- AE
- Concomitant medications
- PGx sample collection (perform only in subjects who consent and from whom the sample has not been collected [see Section 9.1.12])

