7.11.2 Clinical Laboratory Evaluations

7.11.2.1 Hematology and Serum Chemistry

Analysis Set: Safety Analysis Set

Analysis

Variable(s) : Hematology

RBC

WBC

WBC Differentials (Neutrophils, Eosinophils, Basophils, Lymphocytes, Monocytes)

HGB

Hematocrit (HCT)

Platelets

CONFIDENTIAL

Serum Chemistry

ALT	AST	Lactate dehydrogenase (LDH)
Gamma glutamyl transferase (GGT)	Albumin	Alkaline phosphatase (ALP)
Bilirubin (Total bilirubin)	Protein (Total protein)	Cholesterol (Total cholesterol)
High density lipoprotein (HDL) cholesterol	Low density lipoprotein (LDL) cholesterol	Triglycerides
Glucose	HGB A1C	Creatinine
Blood urea nitrogen (BUN)	Creatine kinase	Urate
Sodium	Potassium	Chloride
Calcium	Phosphate	Magnesium

Visit: Baseline , Week 4, 8, 12 and Follow-up

Analytical

Method(s) : For each variable, summaries (1) to (3) will be provided by treatment group.

For applicable variables, summaries (4) and (5) will be provided by treatment group.

(1) Summary of Laboratory Test Results and Change from Baseline by Visit

Descriptive statistics for observed values for each visit and changes from baseline will be provided.

(2) Case Plots

Plots over time for each subject will be presented.

(3) Summary of Shifts of Laboratory Test Results

Shift tables showing the number of subjects in each category at baseline and each post-baseline visit will be provided.

For each laboratory test, the laboratory values will be classified as "Low", "Normal" or "High" relative to the normal reference range provided by the central laboratory. The shift tables will be based on

these classifications.

(4) Number and Percentage of Subjects with Markedly Abnormal Values of Laboratory Parameters

Overall frequency distributions of MAV during treatment period will be provided. If a laboratory parameter has both lower and upper MAV criteria, analysis will be performed for each. Further details are given in Appendix.

(5) Number and Percentage of Subjects with Elevated Liver Enzyme Laboratory Parameters

Overall frequency distributions of elevated hepatic parameters during treatment period will be provided. Further details are given in Appendix.

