23	7.8.1.3Examination of Subgroups Submucosal Fibroid[Yes, No] Cervical Fibroid[Yes, No]	7.8.1.3Examination of Subgroups (削除)	Modified based on the blind review
24	7.8.2.1NRS Score (1)Proportions of subjects with a maximum NRS score of 0 during ...	7.8.2.1NRS Score (1)Proportion of subjects with a maximum NRS score of 0 during ...	Typo
24	7.8.2.1NRS Score (2)For mean NRS score and number of days without pain symptoms (NSR = 0),	7.8.2.1NRS Score (2)For mean NRS score and number of days without pain symptoms (NRS = 0),	Typo

Page	Previous version	Current version	Reason
24	7.8.2.2NRS Score time course Proportion of subjects with a maximum NRS score of 0	7.8.2.2NRS Score time course Proportion of subjects with a maximum NRS score of 1 or less	Typo
25	7.8.2.2NRS Score time course Proportion of subjects with a maximum NRS score of 1	7.8.2.2NRS Score time course Number of days without pain symptoms (NRS = 0)	Typo
25	7.8.2.2NRS Score time course Day 1 to 28, Day 29 to 56, Day 57 to 84	7.8.2.2NRS Score time course Baseline, Day 1 to 28, Day 29 to 56, Day 57 to 84	Based on the comment from team member, added.
25	7.8.2.2NRS Score time course (1)Proportions of subjects with a maximum NRS score of 0 will be summarized by treatment group. The point estimate and 2-sided 95% confidence interval of odds ratio will be calculated between TAK-385 40 mg group and placebo group (TAK-385 40 mg group / placebo group).	7.8.2.2NRS Score time course (1)Proportion of subjects with a maximum NRS score of 1 or less and proportion of subjects with a maximum NRS score of 0 will be summarized by treatment group. The point estimate and 2-sided 95% confidence interval of odds ratio will be calculated between TAK-385 40 mg group and placebo group (TAK-385 40 mg group / placebo group).	Typo
25	7.8.2.2NRS Score time course (2)For mean NRS score and number of days without pain symptoms (NSR = 0),	7.8.2.2NRS Score time course (2)For mean NRS score and number of days without pain symptoms (NRS = 0),	Typo
38	Appendix 1. Criteria for Markedly Abnormal Values up to Follow-up Day 14 will be classified as a MAV or	Appendix 1. Criteria for Markedly Abnormal Values up to Follow-up Day 42 will be classified as a MAV or	Modified based on the comment from team member.

Page	Previous version	Current version	Reason
	not.	not.	

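### The request for a morning, fasted visit stops at VISIT 6, so within-arm Follow-up changes in glucose and triglycerides may partly reflect feeding

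*Protocol*

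**What the plan says.** **Fasting.** Protocol 6.1.1 states: "From VISITS 2 to 6, subjects should try to visit the study site during the morning in a fasted state". The Study Summary (protocol 2.0) and SAP 4.4.1 set the same limit. The visit-day instructions in protocol 7.4 have the same range: "For the scheduled study site visit from VISIT 2 through 6, follow the instructions below".

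**VISIT 7.** Protocol 9.3.4.1 lists clinical laboratory tests among the procedures 28 days after the last dose. It sets no fasting or time-of-day condition.

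**Analytes.** Glucose and triglycerides are in the chemistry panel in protocol Table 9.a and in SAP 7.11.2.1.

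**Analysis.** SAP 7.11.2.1 gives the visits as "Baseline , Week 4, 8, 12 and Follow-up" and says: "Descriptive statistics for observed values for each visit and changes from baseline will be provided". It adds shift tables (low, normal, high) at each post-baseline visit. All of these are by treatment group.

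**Baseline.** Under SAP 7.1.3, the laboratory baseline is the value nearest Day 1 within Day -80 to Day 1. VISIT 3 is Day 1 (protocol 9.3.2.1).

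**The concern.** Glucose and triglycerides respond to food. The sponsor asked for the same conditions at each visit from VISIT 2 to VISIT 6, which includes the usual baseline and Week 12, but not at VISIT 7. The Follow-up column is the only planned look at laboratory values after the drug is stopped. A reader who compares it with baseline or Week 12 within one arm cannot separate a change after withdrawal from a change in whether the subject had eaten. A return towards baseline could be hidden, or a rise could appear that has nothing to do with treatment.

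Laboratory tests are a secondary safety endpoint (protocol 5.2.2), and protocol 6.2.1 says that the Follow-up period is there for safety assessment. The comparison is therefore one that the plan intends to show, although only descriptively.

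**Working it through.** **1. The plan's own figure.** The documents give no figure on this point. Their one design calculation is power above 90% with 28 evaluable subjects per group, 20.0% against 65.0%, two-sided 5% Fisher's exact test. Exact enumeration gives 90.4%, so it reproduces. Nothing below depends on it.

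**2. Conditions at each laboratory sample.**

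| Sample | Morning, fasted visit requested? | Role in SAP laboratory tables |
|---|---|---|
| VISIT 1 | No | Baseline only if no later value up to Day 1 |
| VISIT 2 | Yes | Baseline only if Day 1 is missing |
| VISIT 3 (Day 1) | Yes | Usual baseline |
| VISITS 4 and 5 | Yes | Weeks 4 and 8 |
| VISIT 6 (Day 85) | Yes | Week 12 |
| VISIT 7 (Follow-up Day 28) | No | Follow-up (window Follow-up Days 15 to 42) |

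Only the Follow-up row differs from the usual baseline in what subjects are asked to do.

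**3. Effect on a within-arm mean.** Let *d* be the average rise from a meal and *f* the share of an arm that comes unfasted to VISIT 7. Suppose that baseline was fasted and that the drug has no effect on the analyte.

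Expected within-arm Follow-up change = *f* × *d*

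Both *d* and *f* are assumptions, because the documents give neither:

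| *d* (units) | *f* = 25% | *f* = 50% | *f* = 100% |
|---|---|---|---|
| 10 | 2.5 | 5 | 10 |
| 25 | 6.25 | 12.5 | 25 |
| 50 | 12.5 | 25 | 50 |

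A simulation with 32 subjects per arm and an assumed standard deviation of change of 30 units agreed. For *d* = 25 it gave 6.4, 12.5 and 25.1.

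**4. Effect on the contrast with placebo.**

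Expected difference between arms = *d* × (*f* in TAK-385 arm − *f* in placebo arm)

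With equal shares this is zero, and the simulated differences were all close to 0 (largest −0.18 units, at *d* = 50). It departs from zero only if the shares differ. For example, 50% against 25% with *d* = 25 gives 25 × 0.25 = 6.25 units. Nothing in the documents suggests that the shares would differ.

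**The case against.** The strongest reply is that the placebo arm already deals with this. Both blinded arms have the same VISIT 7 rules and the tables are by treatment group, so a rise from feeding would show in both columns. That stands for the contrast between arms. It does not rescue a within-arm reading, and SAP 7.11.2.1 reports within-arm changes and plans no difference between arms for laboratory values.

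Second, the baseline is not firmly fasted. The request asks subjects only to try. For VISITS 4 and 5, protocol 7.4 says: "If the subject cannot visit the study site in the morning, she must take the TAK-385 tablet before breakfast", so a late arrival may have eaten. This also stands. The plan has a soft request that lapses at VISIT 7, and on-treatment samples are not fully standardised either.

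Third, the request may exist because the tablet is taken before breakfast after the day's tests, and no tablet is due at VISIT 7. That is plausible, but the reason for the request does not make the samples comparable.

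Fourth, protocol Appendix A, the SAP appendices and the Handling Rules for Analysis Data are not in the text reviewed, and one of them could contain a fasting rule. This cannot be excluded. The three matching statements that stop at VISIT 6 make a fasting note for VISIT 7 unlikely. Protocol 7.4 also advises against excess food and drink the day before every visit, which covers VISIT 7 but is not fasting.

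A reader might infer more than the documents support:

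- **That VISIT 7 samples are fed.** They are unstandardised; some subjects may come fasted.
- **That counts of markedly abnormal values are inflated.** SAP 7.13 shows that Appendix 1 now runs "up to Follow-up Day 42 will be classified as a MAV or" not, so the Day 28 sample falls inside the range. But those tables cover only applicable variables, and the criteria are not in the text reviewed, so it is unknown whether glucose or triglycerides have any.
- **That the trial sets out to show metabolic reversal.** No objective or endpoint says so, and the only adverse event of special interest is liver function abnormality.

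**Conclusion.** The point holds as a minor one. Follow-up glucose and triglycerides are sampled without the condition requested at the usual baseline, so their within-arm changes and shifts may partly reflect feeding. The size is unknown. It scales with the share of subjects who come unfasted, and the full meal effect reaches the arm mean only if every subject does. This assumes that most baseline samples were in fact fasted and that no fasting rule sits in the appendices or handling rules.

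The comparison with placebo is not biased if both arms eat alike. The matter is confined to two descriptive safety analytes at one post-treatment visit. The primary endpoint, alpha, power and sample size are unaffected.

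**What to change.** 1. **Protocol 2.0 and 6.1.1, and SAP 4.4.1:** extend the morning, fasted request from VISITS 2 to 6 to VISITS 2 to 7. Add VISIT 7 to the visit-day instructions in protocol 7.4 for attendance and fasting only, since no study drug is taken then.
2. **eCRF:** record fasting status at every laboratory visit. The text reviewed has no such item, and it would also identify late samples at VISITS 4 and 5.
3. **SAP 7.11.2.1:** keep all values in the tables, and flag or separately summarise non-fasted glucose and triglycerides. Excluding them would conflict with SAP 7.1.4, which keeps all available safety data in the tabulations, and could hide a true abnormality.

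The cost is one more fasted morning visit per subject, one data field and a sentence in the SAP. If VISIT 7 has already taken place for most subjects, a table footnote saying that fasting was not requested at Follow-up is enough.

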6.1.2 Dose Level and Regimen

At VISIT 3, subjects will be randomized in a 1:1 ratio to either the TAK-385 40 mg group or placebo group. Study drug (TAK-385 40 mg or TAK-385 placebo) will be administered from the day of VISIT 3 to the day before VISIT 6 (or until early termination) under double-blind conditions.

TAK-385 (or TAK-385 placebo) will be administered daily as a single oral dose before breakfast.

* In addition to Day -80~-26, informed consent may be obtained before Day -80.

**VISIT 2 and 3: On days 1 to 5 of the menstrual cycle

Figure 6.a Schematic of Study Design

6.2 Justification for Study Design, Dose, and Endpoints

6.2.1 Justification for Study Population and Design

Menorrhagia is the most frequent symptom seen in patients with uterine fibroids. Prolonged menorrhagia can induce iron-deficiency anemia. Therefore, menorrhagia is the main cause of QOL deterioration¹.

Pain symptoms are also known to be important factors that impact the patients' QOL. Pain symptoms in patients with uterine fibroids are observed mostly in menstruation period. However, pain symptoms outside the menstruation period are also observed.

As a result of Phase 2 study (TAK-385/CCT-001), the NRS score from Week 6 to 12 was lower in the higher dose of TAK-385 in patients with uterine fibroids. This result showed a trend toward improvement in the NRS score with increasing dose of TAK-385, indicating the possible effect of TAK-385 on pain relief. However, the efficacy for pain symptoms of TAK-385 is still to be further investigated. For this reason, this study is designed as a double-blind, placebo-

controlled, parallel-group comparison to evaluate the effect of TAK-385 on pain relief in patients with uterine fibroids who have pain symptoms.

The Treatment of this study is set as 3 months for efficacy assessment of primary endpoint because period of general presurgical treatment of myomectomy is 3 months². Additionally, the pain symptoms in patients with uterine fibroids seem to be induced by bleeding, thus a period of approximately 3 months was required to assess the pain symptoms as same as the assessment period of the primary endpoint in pivotal Phase 3 (CCT-002). A single-blind treatment period (with placebo) is also included to investigate if there is any potential placebo effect on baseline pain assessment. In addition, the Follow-up is included for safety assessment, including assessment of the recovery of menstruation after completion of treatment with the study drugs.

6.2.2 Justification for Dose Level and Regimen

The efficacy, safety, pharmacokinetics, and pharmacodynamics of TAK-385 10, 20, and 40 mg were evaluated in study TAK-385/CCT-001. For the primary endpoint (proportion of subjects with a total PBAC score of <10 from Week 6 to 12), statistically significant differences were observed in all TAK-385 treatment groups compared to placebo group. The proportion was higher in the TAK-385 40 mg group compared to the other treatment arms, suggesting a dose-response relationship. Similarly, the trend toward improvement with increasing dose was also observed in the secondary endpoints, change in myoma and uterine volumes, blood concentration of HGB and pain symptoms. The common TEAEs were considered to be caused by the pharmacological effect of TAK-385, and their incidence was higher in the TAK-385 treatment groups compared to placebo group. Most of the TEAEs were mild or moderate, and no serious TEAEs considered related to the study drug were observed. A trend toward a decrease in BMD was observed with increasing dose. However, the type, frequency, and intensity of TEAEs and the percent change of BMD were expected to be at a comparable level as that of GnRH agonists; therefore, there seemed to be no clinically serious problem on safety. For these reasons, the dose of 40 mg is considered appropriate for use as the clinical dose of TAK-385 to evaluate the efficacy and safety in subjects with uterine fibroids.

[REDACTED]

TAK-385 will be administered once daily before breakfast.

6.2.3 Justification for Endpoints

6.2.3.1 Primary Endpoint

Pain experienced in patients with uterine fibroids can be categorized as pain caused by bleeding, pain triggered by twisted myoma or pain associated with compression of the organ by enlarged fibroids. Pain can emerge only during menstruation or can be chronic, and the frequency of pain varies among patients. However, in all of the above cases, QOL is most affected by the “grade” of pain in patients with uterine fibroids who have pain symptom. Therefore, assessment of the

CONFIDENTIAL

highest score in pain assessment scale is considered appropriate to evaluate the efficacy of TAK-385. Subjects with a maximum NRS score of ≥ 4 (ie, subjects with at least “moderate” pain symptoms) and who have pain symptoms of at least 2 days, in 1 menstrual cycle just before VISIT 3 will be regarded as possessing pain symptoms associated with uterine fibroids, and can be included into this study. The “proportion of subjects with a maximum NRS score of 1 or less during the 28 days before the final dose of study drug” is to be evaluated as primary endpoint. As for evaluating the improvement of pain symptoms, it is considered to be preferable to confirm the loss of pain symptoms. However, drug therapy for uterine fibroids is not a curative therapy and uterine fibroids would not disappear after TAK-385 administration. Also, it is often difficult for the subjects who have the pain symptoms to distinguish where their pain occurred, and the possibility that some patients record slight uncomfortable feeling as the pain symptoms associated with uterine fibroids is undeniable. From these reasons, it is not necessarily appropriate to set the loss of pain symptoms as primary endpoint to evaluate the pain-ameliorating effect in TAK-385. Therefore, the cut-off value of 1, which is the lowest score of NRS in patients with pain symptoms, was set for evaluating the improvement of pain symptoms. Three or more changes as NRS score could be found by setting this endpoint. Since the average menstrual cycle in Japanese women is 28 days long, the pain score is to be evaluated in 28 days.

For these reasons, “proportion of subjects with a maximum NRS score of 1 or less during the 28 days before the final dose of study drug” is selected as the primary endpoint.

